#### 4.3 Mid-Study Questionnaire (both sites)

At the mid-point of study (month 3), participants will be asked to complete the quality of life/fatigue questionnaire (Triple A QOL questionnaire). This questionnaire can be completed remotely via a web-survey link, on paper (via mail) or in person (if the study mid-point coincides with the participants' second treatment visit or a nutrition intervention visit)..

#### 4.4 Clinic Visit 2

**UW (at Fred Hutch):** Clinic Visit 2 will occur at the end of the study, 6 months after Clinic Visit 1. In preparation for Clinic Visit 2, participants will be mailed (or given) the end of study Food Record (Food Record, Serving size booklet), stool collection kit, and instructions (Triple-A CV2 instructions, Triple-A Stool collection) to prepare for the visit. Participants will be asked to complete the Food Record and collect a small amount of stool, and bring both to Clinic Visit 2. At Clinic Visit 2, study staff will measure weight and waist circumference, conduct a DXA scan and collect fasting blood. Participants will complete the final questionnaires on physical activity and quality of life (Triple-A QOL questionnaire, Triple-A PA questionnaire), and will complete an End of Study questionnaire (Triple-A Exit Survey). Participants assigned to the control arm will also be given a copy all of the intervention materials and the study dietitian will review the materials.

**VAPSHCS (at VAPSHCS):** Clinic Visit 2 will occur at the end of the study, 6 months after Clinic Visit 1. In preparation for Clinic Visit 2, participants will be mailed (or given) the end of study Food Record, stool collection kit, and instructions to prepare for the visit. Participants will be asked to complete the Food Record and bring it to Clinic Visit 2. At Clinic Visit 2, study staff will measure weight and waist circumference, conduct a DXA scan and collect fasting blood. Participants will complete the final questionnaires on physical activity and quality of life (Triple-A QOL questionnaire, Triple-A PA questionnaire). Finally, participants assigned to the control arm will be given a copy all of the intervention materials and the study dietitian will be scheduled for a brief teleconference with the study dietitian to review the materials.

If requested, a participant may receive a copy of their DEXA scan results.

#### 4.5 Consents

Waiver of HIPAA authorization. A waiver of HIPAA authorization will be obtained to allow the UW urology clinic study staff to pre-screen patients for eligibility. A waiver of HIPAA authorization will also be obtained from the VAPSHCS obtained to allow the VA urology clinic study staff to pre-screen patients for eligibility.

Triple-A Consent for contact UW. Potential participants recruited from the UW will be asked to sign a consent for contact to allow their contact information to allow their personal contact information to be sent to the Fred Hutch for recruitment into this study. [No comparable consent is needed for VA participants, since the clinic visits occur at the VA].

Triple-A VerbalConsentScriptPreStudy: Prior to the first study clinic visit, participants will be asked to provide verbal consent to complete pre-visit 1 study activities.

Triple-A UW Consent. At Clinic Visit 1, potential participants recruited from UW will be asked to sign the main study consent to participate in the intervention trial.

A comparable consent will be created for VA patients, which will cover the study activities that take place at the VA. VA participants who are assigned to the diet and exercise intervention will complete those study activities at Fred Hutch, and will be asked to sign a separate consent (see below) to cover these activities.

Triple-A VA Intervention Consent. VA participants assigned to the intervention arm will complete an additional consent to participate in the intervention (diet and exercise instruction) activities that occur at Fred Hutch.

## 4.6 Intervention

Intervention arm participants will attend 10 sessions with a registered dietitian over six-months to receive instruction on a modified-Dietary Approaches to Stop Hypertension (DASH) diet. In addition, participants will attend two one-on-one sessions with an exercise physiologist to receive instruction on aerobic physical activity and strength/resistance training. Participants will also be offered the opportunity to complete up to 21 additional supervised exercise sessions at either the Fred Hutch Prevention Center (PC) or VA Clinical Research Unit (CRU). The following materials will be used to provide Intervention instruction to participants in the Intervention arm: Triple-A Nutrition Intervention; Triple-A PA Intervention; Triple-A Supplemental Nutrition\_V1; Triple-A Supplemental PA\_V1.

### Diet.

One-on-one diet instruction will be provided by the Fred Hutch study dietitian. This instruction will occur either in person at the Fred Hutch PC or, if necessary, via teleconference. The dietary goals are to adopt and maintain a modified DASH eating pattern. The DASH feeding trial was designed to test whether the provided diet would lower blood pressure and serum lipids. The trial diet was high in fruits and vegetables, whole grains, and low in sodium. The preponderance of evidence supports that a DASH eating pattern or a modified-DASH, lowers inflammation, promotes healthy weight and body composition, and reduces T2D and CVD- both common complications that accompany ADT use.

The Triple A Pilot intervention has modified DASH to: 1) limit saturated fat to 7% of total energy. This will be accomplished via substitution with PUFA-rich plant oils; 2) restrict added sugars as DASH made no specific recommendation about added sugars (only sweetened beverages were reduced in DASH); 3) specify that > 75% of grains should be whole grain and 4) advise lean protein with plentiful essential amino acids (especially branched chain amino acids, BCAAs) and to spread the protein intake throughout the day. The protein component is based on BCAAs' well-known role in muscle protein synthesis and to help alleviate the muscle loss that accompanies ADT use. Additionally, skeletal muscle synthesis is more efficient when amino acid intake is spread throughout the day, particularly in older individuals. Sample menus will be provided across a range of estimated daily kcal (e.g., 2000, 2200). Information on the participant's body weight, age and usual physical activity level will be used to calculate an individualized caloric need for weight maintenance for each. This calorie level will be explained to each participant as incorporated into the DASH curriculum and will be updated to accommodate changes to the participant activity level and/or weight as the study progresses. The modified-DASH diet can be adapted to participant food preferences, dietary restrictions, cultural values (e.g. Kosher, Halal) and cost.

Physical Activity. The physical activity goals are to increase daily moderate to vigorous aerobic activity to at least 150 minutes/week; and to engage in strength/resistance training at least three times per week. One-on-one physical activity instruction will be provided by an exercise physiologist at the Fred Hutch PC. In-person training is critical to properly demonstrate safe resistance training and to receive an aerobic prescription suitable for each participant. Learning specific aerobic and resistance exercises will be coupled with behavioral skills instruction in setting and adhering to goals, making active choices, introducing variety and tools for motivation. Study staff have experience working with cancer patients in active treatment. If at any time, participants experience undue fatigue or other treatment-related symptoms, the exercise regimen will be altered as needed. In addition, participants may complete up to 21 supervised (but not one-on-one) exercise sessions at the Fred Hutch PC. Alternatively, the supervised exercise sessions can be completed at the VA Clinical Research Unit (CRU), which is a comparable exercise facility. At each exercise session, study staff will weigh the participant, and participants will record their activities completed (Exercise Training Record within the Triple-A Supplemental PA)

## 4.7 Controls.

Written information (Triple-A Controls) on standard healthy lifestyle recommendations will be provided along with a 20-30 minutes individual session with a dietitian including 1) US Dietary Guidelines ([www.dietaryguidelines.gov](http://www.dietaryguidelines.gov)); 2) Activity goal of 30 minutes of physical activity 5 days/week; and 3) Discussion of the health benefits of weight maintenance.

## 4.8 Compliance.

Compliance to dietary and physical activity goals will be evaluated by weight, which will be measured at each session, check-ins with the study dietitian and exercise physiologist, and self-monitoring through diet (Triple-A diet daily log within the Triple-A Nutrition Intervention) and physical activity tracking (Triple-A PA daily log within the Triple-A PA Intervention). Formal compliance will be assessed by the 4-day food record (Food Record) and exercise questionnaire (Triple-A PA questionnaire).

## 5. DATA COLLECTION

This study involves a total of two participant visits. Study visits will occur at baseline and at the end of study (6-months), where participants will undergo assessments of anthropometrics, collection of fasting blood and completion of study questionnaires. At the mid-study timepoint (month 3) participants will complete questionnaires remotely.

Twelve-hour fasting blood. Fasting blood samples will be collected at baseline and 6 months at the Fred Hutch. Vacutainers will be labeled with participants' study ID and date, processed within 1 hour of collection and stored at -80°C.

Stool sample. Stool samples will be collected by participants at home prior to the clinic visits at baseline and 6 months. Vacutainers will be labeled with participants' study ID and date, stored within 1 hour of receipt at -80°C.

### Questionnaires:

Food Record. All participants will complete a 4-day food record at baseline and 6 months.

Triple-A PA questionnaire. Physical activity will be assessed at baseline and 6 months with a self-administered administered physical activity questionnaire, the Community Healthy Activities Model Program for Seniors Physical Activity Questionnaire for Older Adults (CHAMPS), which assesses a variety of physical activities that are meaningful and appropriate for older adults. For participants assigned to the intervention arm, resistance and aerobic activities will also be documented during supervised exercise sessions.

Triple-A lifestyle questionnaire. Race/ethnicity, education, smoking, alcohol use and family history of prostate cancer will be assessed at baseline only.

Triple-A Exit survey. Participants will be asked about their experience in the study, and for participants in the intervention arm – challenges they experienced with the intervention.

## 5.1 Outcomes

### 5.1.1 Blood Biomarkers

Blood markers of glucose, insulin, hemoglobin A1c, triglycerides and total, LDL- and HLD-cholesterol will be analyzed by the University of Minnesota Advanced Research and Diagnostics Laboratory. Homeostatic model assessment of insulin resistance (HOMA-IR) will be computed from glucose and insulin concentrations.

### 5.1.2 Body Composition and Anthropometrics

Height will be measured at baseline only, and weight and waist (1" above umbilicus) circumferences will be measured at baseline and 6 months. Dual x-ray absorptiometry (DXA) using a GE Lunar DXA will be obtained to measure body fat and lean mass at baseline and 6 months.

### 5.1.3 Patient Reported Outcomes.

Triple-A QOL questionnaire. Patient reported outcomes including quality of life and fatigue will be measured at

baseline, month 3 (mid-study) and at 6 months (end of study). This questionnaire will be based on the Expanded Prostate Cancer Index Composite (EPIC)-26 Short Form, including prostate and ADT specific questions and the Functional Assessment of Chronic Illness Therapy (FACIT) fatigue scale, measuring fatigue.

#### 5.1.4 Microbiome

Stool DNA will be extracted from the stool samples. The gut microbial community will be characterized by sequencing the 16SRNA and comparing the readouts between the intervention and comparison groups.

---

### 6. PARTICIPANT RISKS AND BENEFITS

---

#### 6.1 Potential Risks

1. Participants may experience a little discomfort or have a temporary bruise from having blood drawn. Occasionally a participant may feel lightheaded or feel faint when having blood drawn.
2. Participants in the intervention arm may experience fatigue, muscle soreness, and possible joint or skeletal injury, injury from exercise (such as a fall) or a medical event during exercise at home or in the VA Clinical Research Unit or the Fred Hutch Prevention Center.
3. Participants in the intervention arm may experience fatigue, muscle soreness, and possible joint or skeletal injury or other unspecified medical events.
4. Some participants may feel that coming to clinic visits (including the nutrition and physical activity curriculum training sessions) may be inconvenient and/or burdensome.
5. Other potential risks are associated with the collection of personally identifiable and health information from the subjects, and the potential for financial and/or employment risk, as a breach of confidential information could make it harder for the subject to find health insurance, life insurance, or employment.

#### 6.2 Protection Against Risks

In the event that this research activity results in an injury, medical treatment will be available, including first aid, emergency treatment and follow up care, as needed. All procedures involving blood collection, DXA and anthropometry will be done at the Fred Hutch Prevention Center Clinic. Trained staff will be available to assist should a medical emergency occur. An MD licensed in Washington State is the Prevention Center Director. Participants will be informed in the written consent form that payment for any such treatment must be provided by the individual and/or the individual's insurance company.

1. Blood draws are associated with certain physical risks such as bruising, fainting, or phlebitis. We will minimize these risks by making sure that all blood draws will be conducted by well-trained phlebotomists at the Fred Hutch Prevention Center. Subjects will be asked before the blood draw if they have experienced problems with blood draws in the past and will be offered an opportunity to lie down during the procedure if they wish. In our experience, blood draws performed in this manner are well tolerated, and any side effects are minimal. Participants should be able to tolerate the loss of 10-20 cc of blood without negative health consequences.
2. We will screen participants so that persons with significant cardiovascular disease that would preclude exercise, will be excluded from participation in this study. The risks associated with the exercise intervention will be reduced by proper warm-up/cool-down periods, instruction from a trained exercise specialist at a slow-paced progression which will be determined by the participants' current fitness level and careful monitoring by an exercise specialist. The exercise specialists will teach participants techniques to minimize joint or muscle injury.

In the extremely rare and unexpected event of an emergency while participants are attending to the Fred Hutch Prevention Center, a staff member and study staff will be on hand at all times throughout the visit to call for help as needed, and a physician will be on call. For complications arising among subjects that have left clinical facilities, participants will be provided with the telephone numbers of the study PIs and

the study coordinator and will be encouraged to call with any problems at any time. Participants will be encouraged to call 911 in case a life-threatening emergency occurs; such an event is unlikely, and it would be extremely unlikely to be related to the study procedures.

3. We will make every effort to schedule participants to come to the FHCRC at times that are convenient for them. This includes all sessions with the study dietitian and exercise specialist.
4. To minimize the risk of breach of confidentiality, we will make sure that all health information and records are labeled with a study identification number only. Personally identifiable information will be kept physically separate from any health information, and only one computer file will link the study identification number to the personally identifiable information such as name, address, telephone.

### 6.3 Benefits

The data generated from this proposed research study will provide the data necessary to inform the final design, power, sample size and endpoints for a fully powered randomized controlled trial in newly diagnosed prostate cancer patients receiving RT + ADT.

Our long-term research and clinical goals are to reduce the morbidity and mortality from prostate cancer. This pilot will provide much needed preliminary data to support an R01. We expect that the future R01 RCT results could lead to practice changing paradigms for newly diagnosed prostate cancer patients receiving radiation + ADT as primary curative-intent treatment. Demonstration that the intervention intercepts the abrupt metabolic and physiologic changes could be widely disseminated to allow more men to receive the most effective cancer therapy without compromising their overall health.

### 6.4 Compensation

Participants will be paid \$100 total (25\$ at the baseline visit, and 75\$ at the 6-month visit) to help compensate for time and travel.

### 6.5 Alternatives

Alternatives to participating in this research study include not participating

## 7. DATA ANALYSIS PLAN

This pilot trial tests whether a nutrition and physical activity intervention initiated concurrently with RT+ADT will intercept ADT-induced metabolic and physiologic abnormalities compared to control. We expect clinically meaningful changes in the control arm and minimal to no changes in the intervention arm, as the primary intervention goal is prevention. To test the intervention effects for our aims, we will use this difference in differences approach, which accounts for expected temporal changes in the biomarkers and body composition measures in the control arm.

1. The effects of the intervention on ADT-induced changes in HOMA-IR will be evaluated using linear regression models with adjustment for the baseline biomarker.
2. The effects of the intervention on ADT-induced changes in body weight and composition will be evaluated using linear regression models. Separate models will be fit for each measure, with an indicator variable for study arm (intervention/control) and adjustment for the respective body composition measure.

As exploratory aims, we will explore intervention effects on blood lipids HbA1c, patient reported outcomes and gut microbiome will be evaluated using linear regression models. Separate models will be fit for each biomarker, with an indicator variable for study arm (intervention/control) and adjustment for the respective baseline biomarker. Further adjustment for biomarkers that may have shared biology (i.e. total and LDL cholesterol) and for medication use that could affect biomarker concentrations will be considered.

We expect most potential confounding variables will be evenly distributed between arms at randomization, but

this assumption will be checked prior to analysis. Analyses will follow an intent-to-treat approach; to be  
2-sided and statistical significance will be set at  $P<0.05$ .

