## 7.1 Sample Size

For this pilot trial with a fixed sample size of 20 participants total (10 per arm), we estimate that we will have 80% power to detect a minimum detectable difference in differences in HOMA-IR (intervention effect) between intervention and control participants of 2.6 (HOMA-IR is unitless). Power calculations used R (package::function) stats::power.t.test for t-tests and assumed a standard deviation of 1.4, pre-post correlation of 0.5 and 2-sided  $\alpha=5\%$ .

---

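### With baseline HOMA-IR assumed at 2–5, the P<0.05 criterion for Aim 1 has about 6–17% power at Table 1's expected change; report the estimate and its interval instead

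*Combined protocol and SAP*

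**What the plan says.** Section 7 describes the trial as a test of whether the intervention prevents the metabolic effects of ADT. On what should happen in each arm it states: "We expect clinically meaningful changes in the control arm and minimal to no changes in the intervention arm". HOMA-IR (Aim 1) is analysed by linear regression adjusted for the baseline value. Tests are two-sided, and "statistical significance will be set at $P<0.05".

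Table 1 in Section 2.1 lists the changes expected from starting ADT. For HOMA-IR it gives one figure, +11.6%.

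Section 7.1 fixes the sample at 10 per arm and says "we estimate that we will have 80% power to detect a minimum detectable difference in differences in HOMA-IR" "between intervention and control participants of 2.6". It "assumed a standard deviation of 1.4", a pre-post correlation of 0.5 and a two-sided 5% level. It does not set 2.6 beside Table 1's figure.

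Section 6.3 says the data are to "inform the final design, power, sample size and endpoints for a fully powered randomized controlled trial".

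The documents give no baseline HOMA-IR and do not commit to reporting confidence intervals.

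**The concern.** Sections 2.1 and 7 together define complete success for Aim 1: controls rise by about 11.6% and the intervention arm stays level. The only effect for which Section 7.1 gives power is 2.6 units, and the reader is not told how that compares with 11.6% of a plausible baseline. If 2.6 is several times the expected effect, the stated criterion will usually return a non-significant result for an intervention that works exactly as hoped.

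The stake is interpretation. A non-significant result could be taken as no effect on insulin resistance. A significant one could arise only from an estimate well above the expected effect, which would be a poor effect size to carry into the later trial. The documents do not say that either reading will be made, but the plan does not guard against them.

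**Working it through.** **Inputs from the documents.** 10 per arm; SD 1.4; pre-post correlation r = 0.5; 80% power; two-sided 5% (Sections 7 and 7.1). Expected HOMA-IR change +11.6% (Table 1). Intervention-arm change about zero (Section 7).

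**Assumptions.** Mean baseline HOMA-IR of 2 to 5, because none is given. All 20 men evaluable; any loss lowers power.

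**Step 1. SD of the comparison.** Section 7.1 does not say whether 1.4 is the SD at one time point or the SD of change. Taking it as the former:
- Change score: 1.4 × √(2 × (1 − 0.5)) = 1.40
- Baseline-adjusted: 1.4 × √(1 − 0.5²) = 1.21
- Change score with the correlation left out: 1.4 × √2 = 1.98

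**Step 2. The plan's own figure.** Exact noncentral-t calculation, 10 per arm, 80% power:
- SD 1.40: detectable difference 1.86
- SD 1.21: 1.61
- SD 1.98: 2.62

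The stated SD and correlation do not return 2.6; under them, power at 2.6 would be 97.5%. Leaving the correlation out nearly reproduces it (power at 2.6 is 79.3%). Both readings are carried forward.

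**Step 3. Power at the expected effect.** Expected difference = 0.116 × baseline. Standard error = SD × √(2/10). Power comes from the noncentral t with noncentrality difference ÷ standard error, on 18 df (17 for the adjusted model).

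| Assumed baseline | Expected difference | Change score, SD 1.40 | Adjusted, SD 1.21 | Change score, SD 1.98 |
|---|---|---|---|---|
| 2 | 0.23 | 6.4% | 6.9% | 5.7% |
| 3 | 0.35 | 8.2% | 9.3% | 6.6% |
| 4 | 0.46 | 10.8% | 12.8% | 7.9% |
| 5 | 0.58 | 14.2% | 17.3% | 9.5% |

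Under the stated SD and correlation, the chance of non-significance when the expected change is fully prevented runs from 100 − 17.3 = 83% to 100 − 6.4 = 94%. The difference of 2.6 is 2.6 ÷ 0.58 = 4.5 to 2.6 ÷ 0.232 = 11.2 times the expected effect.

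**Step 4. Dependence on the assumed baseline.** The baseline at which 11.6% equals the detectable difference is:
- 1.61 ÷ 0.116 = 13.9 (adjusted)
- 1.86 ÷ 0.116 = 16.0 (change score)
- 2.6 ÷ 0.116 = 22.4 (the stated figure)

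At a baseline of 10, power is still only 42% (change score), 52% (adjusted) or 24% (SD 1.98). The table holds the SD at 1.4 throughout, so the ratio of SD to mean falls from 1.4 ÷ 2 = 70% to 1.4 ÷ 5 = 28%. If the SD rose with the mean, power at the higher baselines would be lower than shown.

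**Step 5. Smallest observed difference reaching P<0.05.** Critical t × standard error:
- Change score: 2.10 × 1.40 × √0.2 = 1.31
- Adjusted: 2.11 × 1.21 × √0.2 = 1.14

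These are also the 95% CI half-widths. They are between 1.14 ÷ 0.58 = 2.0 and 1.31 ÷ 0.232 = 5.6 times the expected effect.

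**The case against.** **It is a pilot.** The protocol says so, calls its sample size fixed, labels 2.6 a minimum detectable difference rather than a target, and announces a fully powered trial to follow. This stands. A reader might infer that the trial is too small or cannot serve its purpose. The documents do not support that: 20 men can still yield an SD, a correlation and retention data.

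**The plan is not only a test.** Regression with an arm indicator and baseline adjustment yields an adjusted difference and a standard error, from which an interval follows directly. This also stands. A reader might infer that the analysis produces nothing but P values, which goes too far. What is missing is a commitment to make the estimate and interval the result.

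**Planning inputs are partly covered.** A reader might infer that retention, adherence and variability are ignored. Section 6.3 directs the data to design, power and sample size, Section 8.3 reports withdrawals with reasons, and Section 8.4 monitors retention and adherence. Not listing them as analysis outputs is missing detail. How the later trial sets its SD belongs to that trial's protocol.

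**The power figures rest on an assumed baseline.** True, and 6–17% should not be quoted without it. The conclusion is less sensitive, because the mean baseline would have to be about 14–16 before the expected change reached 80% power.

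**The intervention might lower HOMA-IR as well as prevent a rise.** That would enlarge the contrast, but Section 7 gives prevention as the primary goal. At a baseline of 3, 80% power needs a difference of 1.61–1.86, which is 54–62% of baseline.

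**Conclusion.** The point holds as one about the decision criterion, not the sample size. For baselines of 2–5, with the SD of 1.4 and correlation of 0.5 that the protocol states, the two-sided P<0.05 test has about 6–17% power against full prevention of Table 1's expected change. If the change SD is 1.98, power is about 6–10%. A non-significant Aim 1 result is therefore likely but not certain, and would say little about whether the intervention works. The figures assume no dropout, Table 1's change in controls and none in the intervention arm. No reading of the SD reverses the conclusion, and neither does any baseline below about 14.

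**What to change.** In Section 7, make the baseline-adjusted difference between arms in HOMA-IR, with its 95% CI, the primary reported result for Aim 1. State that neither efficacy nor absence of effect will be concluded from the P value alone.

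In Section 7.1, first reconcile 2.6 with the stated SD and correlation, and say which SD the 1.4 is. Then set the detectable difference beside Table 1's 11.6% and give power at that change over a stated range of assumed baselines.

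The cost is wording in two sections. No patients, visits or assays are added. The downside is that the stated design figures will look less favourable.

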STATISTICS Primary Analysis Plan	Linear regression models will test the intervention effects on ADT-induced changes in HOMA-IR ( Aim 1 ), body composition ( Aim 2 ) and metabolic biomarkers, PRO measures and gut microbiome ( Exploratory aims ). Separate models will be fit for each outcome measure, with an indicator variable for study arm (intervention/control) and adjustment for the respective baseline metabolic biomarker, body composition or PRO measure. Further adjustment for biomarkers that may have shared biology (i.e., total and LDL cholesterol) and for medication use that could affect biomarker concentrations will be considered. We expect most potential confounding variables will be evenly distributed between arms at randomization, but this assumption will be checked prior to analysis. Analyses will follow an intent-to-treat approach.
Rationale for Number of Subjects	We have set a sample size of 10 in each of the intervention and control arms for this pilot study, which will provide preliminary data to support an R01.

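### Section 7.1 sizes a difference-in-differences t-test instead of the planned baseline-adjusted regression, and its detectable HOMA-IR difference of 2.6 follows from neither

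*Combined protocol and SAP*

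**What the plan says.** The synopsis (Statistics, Primary Analysis Plan) gives a single model form for the primary and exploratory outcomes. It has an indicator for arm and "adjustment for the respective baseline metabolic biomarker, body composition or PRO measure". Section 7, item 1 repeats this for HOMA-IR, whose intervention effect "will be evaluated using linear regression models with adjustment for the baseline biomarker". The exploratory paragraph of Section 7 also names the baseline value.

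Two pieces of wording in Section 7 do not fit. The paragraph before the numbered items says "To test the intervention effects for our aims, we will use this difference in differences approach" and supports it with a methods reference. Item 2, on weight and body composition, has an arm indicator and "adjustment for the respective body composition measure", without saying that the covariate is the baseline value.

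Section 7.1 takes the sample as fixed at 20, 10 per arm, and says "we will have 80% power to detect a minimum detectable difference in differences in HOMA-IR" of 2.6. It adds: "Power calculations used R (package::function) stats::power.t.test for t-tests", assuming SD 1.4, pre-post correlation 0.5 and a two-sided 5% level. No baseline covariate enters that calculation.

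**The concern.** A difference in differences, analysed by t-test, compares mean change between arms. The planned regression also adjusts for baseline. In a randomised trial both estimate the same between-arm effect, but with different precision, and in any one trial they give different estimates when the arms differ at baseline by chance. A power statement for one does not describe the other.

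The main issue is the number in Section 7.1. If 2.6 is wrong for its stated inputs, the plan misreports what 20 men can detect on its first primary outcome. Section 6.3 says the pilot is meant to inform the power and sample size of a full trial, so an error in method or inputs here could be carried forward. A lesser issue is that the label and the missing word leave room for an analyst to fit something other than the written model.

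**Working it through.** **Inputs (Section 7.1).** n = 10 per arm, SD = 1.4, pre-post correlation r = 0.5, power 80%, two-sided 5%. Stated detectable difference: 2.6.

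**Step 1. Reproduce the plan's figure with its own test.**
- SD of change = SD × √[2(1 − r)] = 1.4 × √1 = 1.4. At r = 0.5 the SD of the measure and the SD of its change coincide, so it does not matter which of the two the 1.4 was meant to be.
- For a two-sample t-test with 10 per arm and 18 df, the noncentral t distribution gives a detectable difference of 1.325 SD at 80% power.
- 1.325 × 1.4 = 1.85. The stated 2.6 is not reproduced.
- Power at a true difference of 2.6 is 97.5%.

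**Step 2. Look for inputs that give 2.6.**
- The SD of change needed is 2.6 / 1.325 = 1.96.
- Correlation 0: SD of change = 1.4 × √2 = 1.98, and 1.325 × 1.98 = 2.62. Power at 2.6 is then 79.3%.
- Variance entered in place of the SD: 1.4² = 1.96, and 1.325 × 1.96 = 2.60.
- A one-sided test (1.62) and the normal approximation (1.75) do not come near it.

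Both routes that reach 2.6 depart from the stated inputs. The documents do not show which, if either, was taken.

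**Step 3. Same inputs, planned model.**
- Residual SD after baseline adjustment = SD × √(1 − r²) = 1.4 × √0.75 = 1.212.
- With 17 df the multiplier is 1.330, so the detectable difference is 1.330 × 1.212 = 1.61. Power at 2.6 is 99.5%.
- Estimating the slope from 20 men inflates the variance by about 1 + 1/(2n − 4) = 17/16 for a normally distributed baseline. That gives 1.61 × √(17/16) = 1.66.
- With correlation 0, the residual SD is 1.4 and the detectable difference is 1.330 × 1.4 = 1.86, or 1.92 with the same inflation. With an SD of 1.4 for the measure, no correlation makes 2.6 right for the planned model.

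| Analysis | r | Detectable difference | Power at 2.6 |
|---|---|---|---|
| Section 7.1 as stated | 0.5 | 2.6 | 80% |
| Change-score t-test | 0.5 | 1.85 | 97.5% |
| Baseline-adjusted regression | 0.5 | 1.61 (1.66 with slope estimated) | 99.5% |
| Change-score t-test | 0 | 2.62 | 79.3% |

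**Step 4. How much the label could matter if taken literally.**
- Variance ratio, adjusted to change score: (1 − r²) / [2(1 − r)] = (1 + r)/2 = 0.75 at r = 0.5, or about 0.75 × 17/16 = 0.80 with the slope estimated.
- The two estimates differ by (1 − r) times the chance difference in mean baseline. The SD of that gap is 0.5 × 1.4 × √(2/10) = 0.31 HOMA-IR units.
- Over assumed correlations from 0.3 to 0.9, the detectable differences run from 2.19 (change score) and 1.78 (adjusted) down to 0.83 and 0.81, so the choice matters less as correlation rises.

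**Step 5. Outcome scale.** Regressing change, or the 6-month value, on arm plus baseline gives the same arm coefficient. In a numerical check both gave −0.700 where the raw difference in mean changes gave −0.158. Leaving the dependent variable open therefore does no harm once baseline is in the model.

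**The case against.** A reader might infer that the plan leaves two competing primary analyses. The documents do not support that. No section specifies an unadjusted comparison of changes as the primary test. The only model written is arm plus baseline covariate. In Section 7, the difference-in-differences sentence follows one that contrasts expected change in controls with little change under intervention, so it can be read as describing that contrast before the numbered items put it into a model. The omission in item 2 is a slip. The synopsis names baseline body composition outright, the neighbouring models say baseline, and adjusting an outcome for itself is not a usable analysis.

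A reader might also infer that the two methods estimate different quantities. Under randomisation they do not. They differ in precision and in the realised estimate.

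It can further be said that the sample is fixed for a pilot, so no enrolment decision rests on 2.6, and that quoting too large a detectable difference errs on the cautious side. Both points stand. They limit the consequence but do not make the figure correct. For Aim 2 the documents give no SD or correlation, so no size can be put on the wording issue there. If pre-post correlation is high for weight and DXA measures, the choice of method would hardly matter.

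**Conclusion.** The point holds as an error in Section 7.1, with minor wording faults beside it. The stated 2.6 is about 1.4 times what the plan's own test and inputs give (2.6 / 1.85) and about 1.6 times what the planned regression gives (2.6 / 1.61). Taken alone, the label and the missing word would be clerical, because the synopsis already settles the model. They belong in the same correction because the label reappears in Section 7.1 as the quantity being powered.

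These figures assume normally distributed HOMA-IR, equal SDs across arms and visits, all 20 men analysed, and the SD and correlation as stated. If either of those inputs was misreported, the size of the discrepancy changes, but Section 7.1 still describes a test other than the planned one.

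**What to change.** - In Section 7, name the regression on arm plus the baseline value of the same measure as the single primary analysis for every outcome. Either change or the 6-month value may be the dependent variable.
- Drop the difference-in-differences label, or state that it means this baseline-adjusted comparison.
- Insert the word baseline in item 2.
- In Section 7.1, restate the detectable HOMA-IR difference for that model: about 1.61 from the stated inputs, or 1.66 allowing for the estimated slope. If SD 1.4 or correlation 0.5 was not the value used, correct it and recalculate for the same model.

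The cost is a few words and one recalculation. No visits, data or participants are added.
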